5.1.1.8 CYP450 Enzyme Normalization

Drug interaction studies have not been conducted with satralizumab. In patients with rheumatoid arthritis who were administered tocilizumab, increased expression of CYP3A4, CYP2C19 and CYP2D6 has been suggested. Reports have suggested that overproduction of IL-6 in patients with inflammatory response inhibits the expression of CYPs. Satralizumab administration may normalize CYP expression and the beneficial effects of concomitant drugs may decrease as the inflammatory reaction improves.

- Patients taking medicinal products which are individually adjusted and are metabolized via CYP450 3A4, 1A2, 2C9 or 2C19 should be monitored as doses may need to be *modified*.

5.1.1.9 Complications of Diverticulitis

To date, gastrointestinal perforations have not been reported in clinical trials with satralizumab treatment.

Gastrointestinal perforations have been reported rarely in patients administered tocilizumab. Although it is unknown whether gastrointestinal perforations are associated with IL-6 inhibition, satralizumab may suppress the acute symptoms (abdominal pain, pyrexia, etc.) associated with diverticulitis, etc., causing delayed diagnosis and progression to perforation.

In this *study*, patients who have a history of active diverticulitis may be precluded from participation.

- Patients presenting with symptoms potentially indicative of complicated diverticulitis, such as abdominal pain, should be evaluated (X-ray, computerized tomography scan, etc.) promptly for early identification of gastrointestinal perforation and appropriate measures taken.

- Patients should be made aware of the symptomatology potentially indicative of complicated diverticular disease, and they should be instructed to alert their physician as soon as possible if these symptoms arise.
- In patients who receive corticosteroids and/or non-steroidal anti-inflammatory drugs, prophylactic treatment with proton pump inhibitor or H2 blocker should be considered

5.1.1.10 Malignancies

No increased risk of malignancies has been observed in clinical trials with satralizumab treatment.

Although malignancies have been reported in patients given tocilizumab, there have been no report to date that tocilizumab appreciably increases the occurrence of malignancies.

All patients with history of malignancy within the last 5 years, including solid tumors, hematologic malignancies and in situ carcinoma (except basal cell and squamous cell carcinomas of the skin, or in situ carcinoma of the cervix uteri that have been completely excised and cured) will be excluded from this study.

Satralizumab should be discontinued in patients with malignancies (with the exception of local basal or squamous cell carcinoma of the skin that is completely excised with free margins)

5.1.1.11 Demyelinating Disorders

Demyelination-related diseases have not been reported in clinical trials with satralizumab treatment.

The impact of treatment with tocilizumab on demyelinating disorders is not known, but multiple sclerosis and chronic inflammatory demyelinating polyneuropathy were reported rarely in RA clinical studies. PML has not been reported.

Patients with evidence of other demyelinating disease or PML will be excluded from this study.

If symptoms suggestive of a demyelination-related disease are observed, differential diagnosis of the cause should be performed.

5.1.2 Other Information

Stevens-Johnson syndrome (SJS) has not been reported in clinical trials with satralizumab treatment.

It is unknown whether SJS is associated with IL-6 inhibition, but SJS has been reported rarely in patients administered tocilizumab.

Patients with a history of SJS will be excluded from this study. Patients must be instructed to contact their physician immediately when any symptoms suggesting SJS appear, in order to assure early diagnosis and appropriate treatment. Satralizumab must not be administered in patients with SJS.

5.2 SAFETY PARAMETERS AND DEFINITIONS

Safety assessments will consist of monitoring and recording AEs, including SAEs, AESIs and selected AEs (see Section 5.2.4); measurement of protocol-specified safety laboratory assessments; measurement of protocol-specified vital signs; and other protocol-specified tests that are deemed critical to the safety evaluation of the study.

Certain types of events require immediate reporting to the Sponsor, as outlined in Section 5.4.

5.2.1 Adverse Events

According to the ICH guideline for GCP, an AE is any untoward medical occurrence in a clinical investigation subject administered a pharmaceutical product, regardless of causal attribution. An AE can therefore be any of the following:

- Any unfavorable and unintended sign (including an abnormal laboratory finding), symptom, or disease temporally associated with the use of a medicinal product, whether or not considered related to the medicinal product
- Any new disease or exacerbation of an existing disease (a worsening in the character, frequency, or severity of a known condition), except as described in Section 5.3.5.9
- Recurrence of an intermittent medical condition (e.g., headache) not present at baseline
- Any deterioration in a laboratory value or other clinical test (e.g., ECG, X-ray) that is associated with symptoms or leads to a change in study treatment or concomitant treatment or discontinuation from study treatment
- Adverse events that are related to a protocol-mandated intervention, including those that occur prior to assignment of study treatment (e.g., invasive screening procedures such as biopsies)

New or worsening neurological symptoms considered NMO-related are not AEs. Clinical relapse will be recorded only on a pre-specified eCRF “NMO relapse” form.

5.2.2 Serious Adverse Events (Immediately Reportable to the Sponsor)

An SAE is any AE that meets any of the following criteria:

- Fatal (i.e., the AE actually causes or leads to death)
- Life threatening (i.e., the AE, in the view of the Investigator, places the patient at immediate risk of death) this does not include any AE that had it occurred in a more severe form or was allowed to continue might have caused death
- Requires or prolongs inpatient hospitalization (see Section [5.3.5.10](#))
- Results in persistent or significant disability/incapacity (i.e., the AE results in substantial disruption of the patient's ability to conduct normal life functions)
- Congenital anomaly/birth defect in a neonate/infant born to a mother exposed to study treatment
- Significant medical event in the Investigator's judgment (e.g., may jeopardize the patient or may require medical/surgical intervention to prevent one of the outcomes listed above)

The exception to this definition of an SAE is in the rare event that a patient is hospitalized following an NMO relapse, as long as the reason for hospitalization is to receive standard treatment with pulse IV corticosteroids and/or apheresis (including plasma exchange and plasmapheresis).

The terms "severe" and "serious" are not synonymous. Severity refers to the intensity of an AE (rated as mild, moderate, or severe] criteria; see Section [5.3.3](#)); the event itself may be of relatively minor medical significance (such as severe headache without any further findings).

Severity and seriousness need to be independently assessed for each AE recorded on the eCRF.

Serious adverse events are required to be reported by the Investigator to the Sponsor within 24 hours after learning of the event (see Section [5.4.2](#) for reporting instructions).

5.2.3 Non-serious Adverse Events of Special Interest (Immediately Reportable to the Sponsor)

Non-serious AESIs are required to be reported by the Investigator to the Sponsor within 24 hours after learning of the event (see Section 5.4.2 for reporting instructions). Non-serious AESIs for this study include the following:

- Cases of an elevated ALT or AST in combination with either an elevated bilirubin or clinical jaundice, as defined in Section 5.3.5.6.
- Suspected transmission of an infectious agent by the study treatment.

5.2.4 Selected Adverse Events

Additional data will be collected for the following selected AEs. The data should be recorded in the eCRF on the AE page and on the special form for that particular AE.

- infections that require treatments with IV antibiotics, antifungals, antivirals
- opportunistic infections that require treatments with oral antibiotics, antifungals, or antivirals
- injection-related reaction (IRR; an AE which occurs within 24 hours after study treatment injection except where the event is not considered an allergic reaction).

5.3 METHODS AND TIMING FOR CAPTURING AND ASSESSING SAFETY PARAMETERS

The Investigator is responsible for ensuring that all AEs (see Section 5.2.1) are recorded on the Adverse Event pages of the eCRF and reported to the Sponsor in accordance with instructions provided in this section and in Sections 5.4–5.6. The Investigator is also responsible for reporting medical device complaints (see Section 5.4.4).

For each AE recorded on the Adverse Event pages in the eCRF, the Investigator will make an assessment of seriousness (see Section 5.2.2 for seriousness criteria), severity (see Section 5.3.3), and causality (see Section 5.3.4).

5.3.1 Adverse Event Reporting Period

Investigators will seek information on AEs at each patient contact. All AEs, whether reported by the patient or noted by study personnel, will be recorded in the patient's medical record and on the Adverse Event pages of the eCRF.

After informed consent has been obtained but prior to initiation of study treatment, only SAEs caused by a protocol-mandated intervention should be reported (e.g., SAEs related to invasive procedures of the protocol). These SAEs will be recorded in the Drug Safety database but not on the Adverse Event eCRF.

After initiation of study treatment, all AEs, regardless of relationship to study treatment, will be reported on the eCRF until the Withdrawal Visit or Last Observation (12 weeks after the last dose of study treatment). After this period, Investigators should report any deaths, SAEs, or other AEs of concern that are believed to be related to prior treatment with study treatment (see Section 5.6).

5.3.2 Eliciting Adverse Event Information

A consistent methodology of non-directive questioning should be adopted for eliciting AE information. Example of non-directive questions includes the following:

“How have you felt since your last clinic visit?”

“Have you had any new or changed health problems since you were last here?”

5.3.3 Assessment of Severity of Adverse Events

Table 5 provides guidance for assessing AE severity.

Table 5 Adverse Event Severity Grading

Severity	Description
Mild	Discomfort noticed, but no disruption of normal daily activity
Moderate	Discomfort sufficient to reduce or affect normal daily activity
Severe	Incapacitating with inability to work or to perform normal daily activity

Note: Regardless of severity, some events may also meet seriousness criteria. Refer to definition of a SAE (see Section 5.2.2).

5.3.4 Assessment of Causality of Adverse Events

Investigators should use their knowledge of the patient, the circumstances surrounding the event, and an evaluation of any potential alternative causes to determine whether or not an AE is considered to be related to the study treatment, indicating "yes" or "no" accordingly. The following guidance should be taken into consideration:

- Temporal relationship of event onset to the initiation of study treatment
- Course of the event, considering especially the effects of dose reduction, discontinuation of study treatment, or reintroduction of study treatment (where applicable)
- Known association of the event with the study treatment or with similar treatments
- Known association of the event with the disease under study
- Presence of risk factors in the patient or use of concomitant medications known to increase the occurrence of the event

- Presence of non-treatment-related factors that are known to be associated with the occurrence of the event

5.3.5 Procedures for Recording Adverse Events

Investigators should use correct medical terminology/concepts when recording AEs on the Adverse Event page of the eCRF. Colloquialisms and abbreviations should be avoided.

Only one AE term should be recorded in the event field on the Adverse Event page of the eCRF.

5.3.5.1 Diagnosis versus Signs and Symptoms

Injection-Related Reactions

Injection-related reaction is defined as the event that occurs within 24 hours after study treatment injection. An IRR should be recorded on the IRR page of the eCRF as “injection-related reaction”, and individual signs and symptoms should also be captured on the IRR page of the eCRF.

But exceptive conditions are as follows:

- Anaphylaxis or anaphylactic shock:
If the event is judged as anaphylaxis or anaphylactic shock by Investigator’s discretion, it will be recorded on the Adverse Event page of the eCRF.
- Obviously not allergic reaction (e.g., infection):
If the event is judged as not allergic reaction, it will be recorded on the Adverse Event page of the eCRF.

Other Adverse Events

For AEs other than injection-related reactions, a diagnosis (if known) should be recorded on the Adverse Event page of the eCRF rather than individual signs and symptoms (e.g., record only liver failure or hepatitis rather than jaundice, asterixis, and elevated transaminases). However, if a constellation of signs and/or symptoms cannot be medically characterized as a single diagnosis or syndrome at the time of reporting, each individual event should be recorded on the Adverse Event page of the eCRF. If a diagnosis is subsequently established, all previously reported AEs based on signs and symptoms should be nullified and replaced by one AE report based on the single diagnosis, with a starting date that corresponds to the starting date of the first symptom of the eventual diagnosis.

5.3.5.2 Adverse Events Occurring Secondary to Other Events

In general, AEs occurring secondary to other events (e.g., cascade events or clinical sequelae) should be identified by their primary cause, with the exception of severe or

serious secondary events. However, medically significant AEs occurring secondary to an initiating event that are separated in time should be recorded as independent events on the Adverse Event page of the eCRF. For example:

- If vomiting results in mild dehydration with no additional treatment in a healthy adult, only vomiting should be reported on the eCRF.
- If vomiting results in severe dehydration, both events should be reported separately on the eCRF.
- If a severe gastrointestinal hemorrhage leads to renal failure, both events should be reported separately on the eCRF.
- If dizziness leads to a fall and subsequent fracture, all three events should be reported separately on the eCRF.
- If neutropenia is accompanied by an infection, both events should be reported separately on the eCRF.

All AEs should be recorded separately on the Adverse Event page of the eCRF if it is unclear as to whether the events are associated.

5.3.5.3 Persistent or Recurrent Adverse Events

A persistent AE is one that extends continuously, without resolution, between patient evaluation time points. Such events should only be recorded once on the Adverse Event page of the eCRF. The initial severity of the event should be recorded, and the severity should be updated to reflect the most extreme severity any time the event worsens. If the event becomes serious, the Adverse Event page of the eCRF should be updated to reflect this.

A recurrent AE is one that resolves between patient evaluation timepoints and subsequently recurs. Each recurrence of an AE should be recorded separately on the Adverse Event page of the eCRF.

5.3.5.4 Abnormal Laboratory Values

Not every laboratory abnormality qualifies as an AE. A laboratory test result should be reported as an AE if it meets any of the following criteria:

- Accompanied by clinical symptoms
- Results in a change in study treatment (e.g., treatment interruption, or treatment discontinuation)

- Results in a medical intervention (e.g., potassium supplementation for hypokalemia) or a change in concomitant therapy
- Clinically significant in the Investigator's judgment

It is the Investigator's responsibility to review all laboratory findings. Medical and scientific judgment should be exercised in deciding whether an isolated laboratory abnormality should be classified as an AE.

If a clinically significant laboratory abnormality is a sign of a disease or syndrome (e.g., alkaline phosphatase and bilirubin 5 times the ULN associated with cholecystitis), only the diagnosis (i.e., cholecystitis) should be recorded on the Adverse Event page of the eCRF.

If a clinically significant laboratory abnormality cannot be related to a disease or syndrome, the abnormality itself should be recorded on the Adverse Event page of the eCRF, along with a descriptor indicating if the test result is above or below the normal range (e.g., "elevated potassium" as opposed to "abnormal potassium"). If the laboratory abnormality can be characterized by a precise clinical term per standard definitions, the clinical term should be recorded as the AE. For example, an elevated serum potassium level of 7.0 mEq/L should be recorded as "hyperkalemia."

Observations of the same clinically significant laboratory abnormality from visit to visit should not be repeatedly recorded on the Adverse Event page of the eCRF, unless the etiology or severity changes. The initial severity of the event should be recorded, and the severity or seriousness should be updated any time the event worsens or improves.

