4.11.3 Adverse Events

Adverse events will be coded using MedDRA. All summaries will be sorted alphabetically by System Organ Class (SOC) and preferred term (PT), starting with the most frequent event. All adverse events reported in whole study will be reported in listings. For AEs, if the AE intensity is missing, the worst case (severe) will be assumed. If the drug relationship is missing, the worst case (drug related) will be assumed. In summaries, multiple occurrences of the same PT event in one individual will be counted only once.

The following summary tables of AEs will be provided:

- An overall summary of AEs will be presented. It will include the number and percentage
 of subjects with at least 1 AE, serious AE, AE leading to early discontinuation, adverse
 drug reaction, and severe AE and number of death.
- A summary of AEs by SOC and PT.
- A summary of AEs by Intensity, SOC and PT.
- A summary of AEs leading to discontinuations of treatment.
- A summary of AEs leading to dose interruption.
- A summary of adverse drug reactions (ADRs) by SOC and PT.
- A by-subject listing of all AEs.
- A by-subject listing of all AEs leading to discontinuation.
- A by-subject listing of all AEs leading to drug interruption.
- A by-subject listing of all ADRs.

TP-GDO-WW-016-01
Effective Date: 28Aug13
Related to: SOP-GDO-WW-019

Confidential Version 7.0 Version Date: 28NOV2018

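### Protocol 5.3.5.4 and 5.3.5.5 allow the severity of a laboratory or vital-sign AE to be lowered on improvement, and SAP 4.11.3 has no maximum-intensity rule, so peak severity can be lost from the AE tables

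*Protocol*

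**What the plan says.** Three recording rules and one set of tabulation rules bear on the point.

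- **Protocol 5.3.5.3 (persistent AEs).** The event is entered once, and "the severity should be updated to reflect the most extreme severity any time the event worsens". Seriousness moves in one direction only: the page is updated if the event becomes serious.
- **Protocol 5.3.5.4 (laboratory values).** Repeat observations of the same abnormality "should not be repeatedly recorded on the Adverse Event page of the eCRF, unless the etiology or severity changes". The initial severity is entered, and then "the severity or seriousness should be updated any time the event worsens or improves".
- **Protocol 5.3.5.5 (vital signs).** The update rule and the exception for a change in etiology or severity are the same as in 5.3.5.4.
- **SAP 4.11.3.** The planned outputs include "A summary of AEs by Intensity, SOC and PT" and an overall summary with lines for serious and severe AEs. On repeats, "multiple occurrences of the same PT event in one individual will be counted only once". On gaps, "if the AE intensity is missing, the worst case (severe) will be assumed". No sentence says that the highest intensity is used. Protocol 6.6 calls for AEs by severity grade and does not say so either.

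**The concern.** A table of AEs by intensity is normally read as showing the worst grade each patient reached. That holds only if the worst grade is still on the record when the table is made, or if the analysis recovers it. Here the general rule preserves the peak, while the rule for laboratory and vital-sign events provides for lowering it.

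These events matter for this drug. Protocol 5.1.1 lists neutropenia, thrombocytopenia and liver-enzyme elevation for special attention, and 5.1.1.2 to 5.1.1.4 report such changes with satralizumab in the Phase 3 studies. If peak severity is not reliably kept, the intensity table and the severe-AE count may understate them, and sites may differ in how they record the same course.

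**Working it through.** No arithmetic applies and the plan states no figure to reproduce. The check is to follow one event through the rules: a laboratory AE judged severe at onset, later mild, then resolved.

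1. **Rule of 5.3.5.3.** There is one record, held at severe. The patient appears in the severe row of the intensity table and in the severe-AE line.
2. **5.3.5.4 read as overwriting.** There is one record, changed from severe to mild. The event stays in the intensity table but moves to the mild row, and the patient leaves the severe-AE line unless another severe event keeps them there.
3. **5.3.5.4 read as adding a record.** The exception for a severity change is taken to permit a second entry. A severe and a mild record now exist under one preferred term. The severe-AE line counts patients with at least one such event, so it should still include this patient. The row of the intensity table is undefined, because SAP 4.11.3 counts the term once and does not say which record supplies the intensity. This reading also conflicts with the single-entry rule of 5.3.5.3.

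Next, does anything in the SAP repair readings 2 or 3?

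- The worst-case rule covers missing intensity only. A downgraded intensity is not missing.
- The count-once rule removes duplicates but does not rank them.
- Protocol 7.1 keeps corrections in the audit trail, but no planned output draws on it.

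Finally, what do the laboratory outputs still show?

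- **AST and ALT (SAP 4.11.11).** These are categorised by maximum post-baseline level, with each patient at the highest category reached. Peak liver enzymes are therefore kept.
- **Marked abnormalities (SAP 4.11.10 and Appendix 7.5; Protocol 6.6).** These are listed and counted from laboratory data whatever the AE severity field says. For neutrophils the lower limit is 1.50 x 10^9/L, that is 1,500/uL, with a decrease of at least 20%. The flag catches deep values but does not separate them at the 1,000/uL and 500/uL boundaries of Protocol Table 2.
- **Shift tables (SAP 4.11.10).** These compare baseline with the value at the end of the double-blind period, so a nadir that has recovered need not appear.
- **Neutrophils and platelets.** SAP 4.11 specifies no maximum-change table for them like the one for AST and ALT.

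These outputs partly preserve peak laboratory values. None of them carries AE severity.

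**The case against.** The strongest reply is that the text need not mean overwriting. The exception for a severity change can be read as allowing a fresh entry, in which case the severe record survives. That is a fair reading, and it rules out treating the loss as certain. It does not settle the point, because the intensity then tabulated is undefined and nothing tells sites which reading to use.

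A reader might infer four stronger claims that the documents do not support.

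- **That most neutropenia events are affected.** Protocol 5.1.1.2 says most neutrophil decreases did not persist, but it describes laboratory decreases, not severe AEs. Not every abnormality is an AE (5.3.5.4). Severity is graded by effect on daily life, with severe defined as "Incapacitating with inability to work or to perform normal daily activity" (5.3.3), so a low neutrophil count is not in itself a severe AE. An event that resolves and recurs is recorded afresh each time (5.3.5.3).
- **That the understatement falls mainly on satralizumab.** Sections 5.1.1.2 to 5.1.1.4 give no placebo rates and no counts of severe laboratory AEs for these changes.
- **That serious-AE counts are biased downward.** The wording would permit a seriousness flag to be lowered, and that should be closed off. But under 5.2.2 an AE is serious if it meets any criterion, which later recovery does not undo, and 5.4 requires separate reporting within 24 hours. No bias is shown.
- **That a deep neutropenia would be hidden from the safety report.** The marked-abnormality outputs remain, and AEs leading to interruption or discontinuation have their own summaries in SAP 4.11.3.

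**Conclusion.** The point holds as an inconsistency with a possible effect on two safety outputs. Protocol 5.3.5.4 and 5.3.5.5 contradict 5.3.5.3 on what happens when a laboratory or vital-sign AE improves, and SAP 4.11.3 has no rule that secures the peak. Under the overwriting reading, both the intensity table and the severe-AE count can understate peak severity. Under the added-record reading, only the intensity table is left undefined.

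The size cannot be stated. It depends on how many such AEs were judged severe and then improved while still open, and on how sites applied the sentence. The documents give neither, nor a split by arm. The conclusion assumes only that some sites may have followed the update sentence as written. It does not bear on efficacy or on the laboratory data themselves.

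**What to change.** 1. In Protocol 5.3.5.4 and 5.3.5.5, adopt the rule of 5.3.5.3: keep the most extreme severity, and do not remove seriousness once a criterion was met. State whether a severity change opens a new record.
2. In SAP 4.11.3, state that each patient is counted at maximum intensity per preferred term.
3. For data already collected, search the eCRF audit trail for laboratory and vital-sign AEs whose severity or seriousness was lowered, and tabulate them at the highest recorded grade. Raise site queries where the trail is unclear.

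Steps 1 and 2 take a few sentences, although Protocol 9.5 requires ethics approval for the amendment. Version 10 came after the end of the double-blind period, so step 1 can change recording only in the extension. The placebo-controlled data depend on steps 2 and 3. Sites own data entry and the resolution of discrepancies (Protocol 7.1), so step 3 may involve more than a single query, but the work remains a small data review.
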